5.1.2.2 Assessment of Causal Relationship

The Investigator will assess and record the causal relationship between the AE and the study drug using the following definitions:

- Probable: the AE has a strong temporal relationship to the study drug, and another etiology is unlikely or significantly less likely.
- Possible: the AE has a suggestive temporal relationship to the study drug, and an alternative etiology is equally or less likely.
- Not related: the AE has no temporal relationship to the study drug or is due to underlying/concurrent illness or effect of another drug (that is, there is no causal relationship between the study drug and the adverse event).

An AE will be considered causally related to the use of the study drug when the causality assessment is probable or possible.

5.1.2.3 Assessment of Outcome

The Investigator will assess and record the outcome of the AE using the following definitions:

- Recovered: the subject has recovered completely, and no symptoms remain.
- Recovering: the subject's condition is improving, but symptoms still remain.
- Recovered with sequelae: the subject has recovered, but some symptoms remain
- Not recovered: the subject's condition has not improved and the symptoms are unchanged
- Death

5.2 Pregnancy

Risk Summary

There are no adequate data on the developmental risk associated with the use of AUSTEDO in pregnant women. Administration of AUSTEDO to rats during organogenesis produced no clear adverse effect on embryofetal development. However, administration of tetrabenazine to rats throughout pregnancy and lactation resulted in an increase in stillbirths and postnatal offspring mortality. In the U.S. general population, the estimated background risk of major birth defects and miscarriage in clinically recognized pregnancies is 2-4% and 15-20%, respectively. The background risk of major birth defects and miscarriage for the indicated population is unknown.

Data

Animal Data

Oral administration of AUSTEDO (5, 10, or 30 mg/kg/day) or tetrabenazine (30 mg/kg/day) to pregnant rats during organogenesis had no clear effect on embryofetal development. The highest dose tested was 6 times the maximum recommended human dose of 48 mg/day, on a body surface area (mg/m2) basis. The effects of AUSTEDO when administered during organogenesis to rabbits or during pregnancy and lactation to rats have not been assessed. Tetrabenazine had no effects on embryofetal development when administered to pregnant rabbits during the period of organogenesis at oral doses up to 60 mg/kg/day. When tetrabenazine was administered to female rats (doses of 5, 15, and 30 mg/kg/day) from the beginning of organogenesis through the lactation period, an increase in stillbirths and offspring postnatal mortality was observed at 15 and 30 mg/kg/day, and delayed pup maturation was observed at all doses.

A pregnancy is not an AE. If a subject becomes pregnant while enrolled in the study following administration of study drug, the Sponsor or designee will be notified within 24 hours of the Investigator learning of the pregnancy. Administration of study drug will be discontinued immediately and the subject will be followed through the outcome of the pregnancy.

5.3 Recording Adverse Events

Adverse events will be recorded on an Adverse Event Documentation Form (see Figure 1). The investigator will provide information on the AE, preferably with a diagnosis, or at least with signs and symptoms; start and stop dates, start and stop time; intensity; causal relationship to study drug; action taken; and outcome. If the AE is an overdose, the nature of the overdose will be stated (medication error, accidental overdose, or intentional overdose). If the AE is serious, this will be indicated on the Adverse Event Form. Furthermore, the Investigator will report the SAE to Teva within 24 hours after becoming aware of it.

5.4 Reporting Serious Adverse Events

The Investigator will report SAEs to Teva immediately (within 24 hours) after becoming aware of them by completing a Serious Adverse Event Form. As much information as possible will be recorded. If more information about the patient's condition becomes available at a later date, the Serious Adverse Event Form will be updated with the additional information. Teva will assume responsibility for reporting SAEs to the authorities in accordance with U.S. regulations.

5.5 Treatment and Follow-Up of Adverse Events

Subjects with AEs will be treated in accordance with usual clinical practice at the discretion of the investigator. At the post treatment evaluation, information on new SAEs, if any, and stop dates for previously reported AEs will be recorded. It is the responsibility of the Investigator to follow up on SAEs

until the patient has recovered, stabilized, or recovered with sequelae. Relevant information includes discharge summaries, autopsy reports, and medical consultations.

5.6 Stopping Rule

A study subject will be asked to discontinue study drug if at any point during the trial he or she is found on ECG to have developed a QTc> 500 milliseconds or a QTc increase of >60 milliseconds from baseline. Study subjects will be asked to come in for an Early Termination Visit within 3 business days of study drug discontinuation.

- 6. DATA ANALYSIS / STATISTICAL METHODS
- 6.1 Data Summary
- 6.1.1 Summary of Safety Data

The safety analysis population will include all enrolled subjects who receive at least one dose of study drug. Demographic data and key baseline characteristics will be summarized for the Safety population. Safety data will be summarized from the time of first dose and include all available safety data.

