1.3.1 Selection of AUSTEDO Dose and Schedule of Administration

AUSTEDO is available in 6, 9 and 12 mg tablets. To allow a precise dose titration among study subjects, only 6 mg tablets will be used in the AUDYT trial. As this is an open label trial, all subjects will receive the study drug; there is no placebo arm. All subjects will be instructed to take AUSTEDO with food, and not to chew, crush or break the tablets. The trial will consist of 3 periods:

1. Ramp-up period: During this titration period, AUSTEDO will be started at 12 mg/day and increased up to 48 mg/day for most study subjects, up to 36 mg/day for study subjects receiving a strong CYP2D6 inhibitor, or up to the maximum, well-tolerated dose for those subjects unable to tolerate the maximum recommended dose of AUSTEDO. Dose-limiting toxicity will be defined in this protocol as the development of any of the following during the titration period: a) new or worsening depression, b) worsening of dystonic symptoms, c) QTc increase of >39 but <60 milliseconds from baseline, or d) any other sign or symptom that, at the PI's discretion, would preclude further safe titration of the study drug. AUSTEDO will be increased by 6 mg/week as recommended in the package insert,³ as shown in Table 2 below:

Table 2
Recommended AUSTEDO titration

	Total daily dose (mg)
Week 1	12
Week 2	18
Week 3	24
Week 4	30
Week 5	36
Week 6	42
Week 7	48

- 2. Maintenance period: Once on the maximum dose, subjects will complete 6 weeks of treatment on that dose, unless a side effects ensues. If so, it will remain at the investigator's discretion whether to discontinue the study drug, or to reduce the dose to a new, maximum, well-tolerated dose, on which the study subject will complete 6 weeks of treatment. Details on dose reduction will be discussed further elsewhere in this protocol.
- 3. Post treatment period: Following 6 weeks of treatment with AUSTEDO, the medication will be discontinued and a final safety evaluation will be performed once the subject has been 1 week off study drug.
- 2. TRIAL OBJECTIVES
- 2.1 Primary Objective

To explore the safety and tolerability of the daily oral administration of AUSTEDO in adult study subjects with dystonia.

- 2.2 Secondary Objectives
 - 1. To establish the degree of symptomatic effect of AUSTEDO as measured by the Clinical Global Impression of Improvement Scale (CGI-I) after 6 weeks of AUSTEDO 48 mg daily, or at the highest tolerated dose.

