3.4.3 Duration of Subject Participation

The duration of study participation will be 13 weeks from screening (Week 1) to the post treatment evaluation (Week 13). Treatment period from drug initiation to final on-treatment Visit will be 12 weeks, or less, as follows:

- Study subjects able to titrate up to 48 mg/day will have 6 weeks of ramp-up and 6 weeks of maintenance.
- Study subjects receiving a strong CYP2D6 inhibitor will only be allowed to titrate AUSTEDO up to a dose of 36 mg/day. They will have will have 4 weeks of ramp-up and 6 weeks of maintenance, for a total of 10 weeks on treatment. The total study duration for these subjects will be 11 weeks, when the final post treatment evaluation is included.
- Study subjects who experience dose-limiting side effects will be maintained on their maximum tolerated dose. Once the maximal dose is established for a study subject, they will complete 6

- continuous weeks on this dose (maintenance period), followed by a 1-week washout. For these study subjects, the 6 weeks of maintenance will start once they reduce the study drug to the maximum well-tolerated dose, independent of the duration of the ramp-up period.
- The duration of the trial for study subjects who experience dose-limiting side effects that arise during the ramp-up period will depend on the dose at which the side effects appear. For these subjects, maintenance will continue to last 6 weeks, and they will also have a 1 week washout.
- Premature, unexpected withdrawal from the trial will shorten study duration for that subject in unpredictable ways; subjects will be asked to undergo an early termination safety Visit, whenever possible.

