3.5.1.4 Visit 4: Maintenance dose ends

Visit 4 will happen during the last week of the maintenance period: during week 12 for subjects on 48 mg/day of AUSTEDO, during week 10 for those subjects receiving a strong CYP2D6 inhibitor, and 6 weeks after the initiation of the maintenance period for subjects who experienced dose-limiting side effects during the ramp-up period. This will be the last visit while on study drug, and at this time

subjects will be instructed on when to stop AUSTEDO. According to the package insert,³ treatment with AUSTEDO can be discontinued without tapering. The activities to be performed during Visit 4 include:

- Adverse events will be assessed
- Vital signs
- 12-lead ECG
- C-SSRS
- SSS
- MMSE
- Second video of the movement disorder examination
- MDS-UPDRS Part III
- Patient Global Impression of Improvement
- 3.5.1.5 Visit 5: Post treatment evaluation

Visit 5 will be scheduled 1 week (or up to 9 days, if necessary) after study drug cessation. This is a safety Visit. The activities to be performed during Visit 5 include:

- Adverse events will be assessed
- Complete physical exam
- Vital signs
- 12-lead ECG
- C-SSRS
- SSS
- Returned bottles will be collected and compliance will be assessed
- 3.5.2 Special situations that could cause changes in Study Visit Schedule
- 3.5.2.1 Shortened Ramp-up Period

There are three scenarios that could shorten the duration of the ramp-up period:

- 1. Study subjects taking a strong CYP2D6 inhibitor: The maximum dose of AUSTEDO allowed for subjects taking a strong CYP2D6 inhibitor will be 36 mg/day. These study subjects will start AUSTEDO at 12 mg/day and increase at weekly intervals in increments of 6 mg per day up to 36 mg/day, if tolerated, as instructed in the package insert.³ For these subjects, the maximum length of the ramp-up period will be 4 weeks.

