- 2. Subjects unable to titrate up to the maximum recommended dose: Whether it is 48 mg/day or 36 mg/day, study subjects may experience dose-limiting side effects that do not allow them to titrate up to their individual, maximal recommended dose. Any side effects encountered during the ramp-up period will be recorded and reported as appropriate. Study subjects who encounter these side effects will be instructed to reduce the total daily AUSTEDO dose by 6 mg (1 tablet) every day until a new, maximum well-tolerated dose of AUSTEDO is established. A faster dose reduction will be allowed if deemed necessary by the investigator. Once this new dose is determined, the maintenance period will be considered initiated and subjects will be asked to complete Visit 3 at the study site within 3 days.
- 3. Subjects unable to tolerate 12 mg/day of AUSTEDO: Subjects who are unable to tolerate the starting dose of the study drug will be withdrawn from the trial. Side effects encountered will be recorded and reported as appropriate.
- 3.5.2.2 Early Termination

If at any time during the study a patient requests to withdraw from treatment, or if a decision is made to withdraw the patient from the study, the patient will be requested to return for an Early Termination Visit.

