3.5.2.5 Subject Withdrawal

Subjects will be advised that they are free to withdraw from the study at any time. Reasons that subjects may be withdrawn from the study include the following:

• Subject discontinued study medication: according to the package insert,³ following treatment interruption of greater than one week, AUSTEDO therapy would need to be re-titrated when resumed, and, thus, subjects who require drug cessation for a week or more will be considered

withdrawn from the trial. For treatment interruption of less than one week, treatment can be resumed at the previous maintenance dose without titration, as per the package insert.³

- Subject consent is withdrawn
- QTc changes: A study subject will be asked to discontinue study drug if at any point during the trial he or she is found on ECG to have developed a QTc> 500 milliseconds or a QTc increase of >60 milliseconds from baseline.
- Sponsor decision, after discussion with the Investigator

If a subject is withdrawn from the study, all efforts will be made to complete the early termination Visit that includes efficacy assessments and safety follow-up. In addition, women of childbearing potential will have a pregnancy test performed at the early termination Visit. All information, including the reason for withdrawal, will be reported. For subjects who are lost to follow-up, three recorded attempts will be made to contact the subject for follow-up information, including reason for discontinuation and follow-up of AEs. Subjects who withdraw from the study will not be replaced.

- 3.6 Study Procedures and Assessments
- 3.6.1 Safety assessments
- 3.6.1.1 Adverse Events

During the study, the Investigator or study site personnel will be responsible for querying and recording adverse events (AEs) and serious adverse events (SAEs). In this study AEs and SAEs will be reported from the time of study drug administration until Visit 5 or death, whichever occurs first.

An adverse event (AE) is any untoward medical occurrence that occurs in conjunction with the use of a medicinal product in humans, whether or not considered to have a causal relationship to the medicinal product. According to the package insert,³ adverse reactions experienced by at least 4% of subjects on AUSTEDO and with a greater incidence than on placebo include somnolence, diarrhea, dry mouth, fatigue, urinary tract infection, insomnia, anxiety, constipation and contusion.

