Table 6 below shows a list of medications that are known to prolong the QTc. Subjects taking these medication will be allowed to participate in the trial as long as their ECG during visit 1 (and while already on one or more of these drugs at steady state) shows no QTc prolongation. Any evidence of QTc prolongation during subsequent ECGs will require an adjustment in the AUSTEDO dose as detailed elsewhere. The introduction of these medications will not be allowed for the duration of the trial. If it is determined that a subject requires one of these medications during their participation in the trial, AUSTEDO will be stopped and the subject will be considered withdrawn from the trial.

Table 6 Drugs causing QTc prolongation
Moxifloxacin
Quinidine
Procainamide
Amiodarone
Sotalol

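### Subjects who leave early have no dated safety contact after the early termination visit, while those who finish treatment are seen 7–9 days off drug (low priority, cheap to fix)

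*Combined protocol and SAP*

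**What the plan says.** For subjects who finish treatment, section 1.3.1 states that "a final safety evaluation will be performed once the subject has been 1 week off study drug", and section 3.5.1.5 sets the timing: "Visit 5 will be scheduled 1 week (or up to 9 days, if necessary) after study drug cessation". That visit includes AE review, a physical examination, vital signs, an ECG, the C-SSRS and a sleepiness scale.

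For early leavers:

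- **QTc stop (3.6.1.2 and 5.6).** After a QTc above 500 ms or a rise above 60 ms: "Study subjects will be asked to come in for an Early Termination Visit within 3 business days of study drug discontinuation".
- **Withdrawal in general (3.4.3, 3.5.2.2, 3.5.2.5).** Section 3.5.2.2 says "the patient will be requested to return for an Early Termination Visit". Section 3.5.2.5 says "all efforts will be made to complete the early termination Visit that includes efficacy assessments and safety follow-up". Section 3.4.3 says "subjects will be asked to undergo an early termination safety Visit, whenever possible". None gives a date.
- **Need for a QTc-prolonging drug (4.8).** "AUSTEDO will be stopped and the subject will be considered withdrawn from the trial". No timing is attached.
- **Loss to follow-up (3.5.2.5).** "three recorded attempts will be made to contact the subject for follow-up information, including reason for discontinuation and follow-up of AEs". These attempts are undated.

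Appendix 1 gives the early termination visit its own column, with every safety item of Visit 5. Nothing in the text or the schedule sends an early leaver on to Visit 5 or to another dated contact.

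AE reporting ends at Visit 5 or death in section 3.6.1.1, and at the last study visit or death in section 5.1.1.

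**The concern.** The plan sets its own standard for off-drug safety observation, about one week, and applies it only to subjects who finish. A subject who stops early can attend the early termination visit on or near the stop day and then have no further scheduled contact. A new event in the following days is captured only if the subject reports it unprompted, whereas a subject who finished would be asked about it.

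Safety and tolerability are the primary objective. With 15 subjects, AEs will be read one subject at a time, and early leavers are plausibly among the more informative. Uneven ascertainment between finishers and leavers is therefore worth removing if that is cheap.

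The two descriptions of the AE window agree for finishers. For an early leaver, who has no Visit 5, only the section 5.1.1 wording works, and it closes the window at the early termination visit.

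**Working it through.** The plan states no figure on this point to reproduce. The check covers timing, residual drug, existing cover and numbers.

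**1. Calendar days in the QTc window.** With a Monday–Friday working week and no public holiday, three business days after the stop is:

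| Stop day | Latest visit (calendar days) |
|---|---|
| Sunday, Monday, Tuesday | 3 |
| Saturday | 4 |
| Wednesday, Thursday, Friday | 5 |

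The wording does not exclude a same-day visit, so the range is 0–5 days. Against day 7, a visit at the limit falls 7 − 5 = 2 to 7 − 3 = 4 days short. A same-day visit falls 7 days short. For other routes the shortfall cannot be computed, because no window is given.

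**2. Active metabolite remaining.** Section 4.1.4 gives a half-life of 9–10 hours. Fraction remaining after d days = 0.5^(24d / half-life):

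| Day | 9 h | 10 h |
|---|---|---|
| 0 | 100% | 100% |
| 1 | 15.7% | 18.9% |
| 2 | 2.5% | 3.6% |
| 3 | 0.39% | 0.68% |

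An assessment at the 3-business-day limit is effectively off drug. One on day 0 or 1 is not.

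Section 4.8 reports about three-fold exposure with a strong CYP2D6 inhibitor. If all of that is reduced clearance at constant volume (an assumption the documents do not make), the half-life is 27–30 hours. The fraction left is then 54–57% on day 1, 16–19% on day 3, 5–6% on day 5 and 1–2% on day 7.

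**3. What is already covered, by route.**

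| Route | Follow-up already in the plan |
|---|---|
| Withdrawal because of an AE | Followed until it resolves or settles at a new baseline (5.1.1) |
| QTc stop | Usually an AE under 5.1.1, so as above |
| Suicidality stop | Usually as above, plus psychiatric care as needed (3.6.1.5) |
| Any serious AE | Followed to recovery or stabilisation (5.5) |
| Off drug a week or more | Withdrawal rule applies from day 7, so the visit may already be late enough (3.5.2.4) |
| Own request, sponsor decision, need for a QTc-prolonging drug | Early termination visit, then nothing dated |

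The AE and serious-AE duties concern events already known. They do not arrange for anyone to ask about new ones. The uncovered case is a new event after an early termination visit held before day 7, mainly in the last row.

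**4. How many subjects.** In the Huntington trial described in section 1.2.2, 87 of 90 completed: (90 − 87)/90 = 3.3%, and 0.033 × 15 = 0.5 early leavers. At an assumed 20%, 0.20 × 15 = 3. Both figures count leavers from any cause. The uncovered group also needs a visit before day 7 and a later new event, so it is smaller; the documents give no rate for it.

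**The case against.** The strongest objection is that the only dated rule, the QTc stop, belongs to one of the best-protected routes. A QTc above 500 ms or a rise above 60 ms meets the broad AE definition in section 5.1.1, and follow-up to resolution or a new baseline is open-ended and stronger than a single call. The same applies to most suicidality stops. This stands. A reader might infer that subjects stopped for QTc or suicidality go unobserved; the documents do not support that.

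Second, a same-day visit is an edge case. Subjects are asked to come in, or to return, after stopping, which most naturally means a separate later visit, and by day 3 little drug remains in most subjects. This stands for QTc stops. It helps less for the other routes, where no date is set.

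Third, section 3.5.1.4 notes from the package insert that the drug can be stopped without tapering, which weakens the case for a check in the withdrawal period. That is fair, but finishers also stop without tapering and the plan still sees them a week later.

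Fourth, the early termination visit is a full safety visit, unscheduled visits are allowed (3.5.2.3), and all available safety data are summarised (6.1.1). So visit content is not the problem. A discretionary visit, or a summary of what was collected, does not replace asking.

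Finally, closing scheduled follow-up at a full visit, with event-driven follow-up afterwards, is a defensible choice for a 15-subject pilot of a marketed drug. That limits the priority of the point but does not remove the difference between finishers and leavers.

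**Conclusion.** The gap is real but small: a low-priority, inexpensive improvement. Finishers are asked about AEs and have the C-SSRS 7–9 days off drug. An early leaver's last scheduled contact is 0–5 days after a QTc stop and undated otherwise. What is not guaranteed is capture of new-onset events after an early termination visit before day 7, mainly in leavers without an ongoing AE.

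The number affected is unknown and lies below the all-cause 0.5–3 of 15, where the 3 rests on an assumed 20% rate. The 0–5 day range assumes no public holiday; one in the window makes it 6.

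A reader might infer that the primary result is biased. It is not: an early leaver already counts as not completing at the target dose. Nor should the chance of having any early leaver be read as the size of the gap, since most routes out of the trial carry some follow-up. The two AE-window wordings need aligning for leavers, but they do not conflict for subjects who finish.

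**What to change.** 1. In sections 3.5.2.2 and 3.5.2.5 and in Appendix 1, add: *If the Early Termination Visit takes place less than 7 days after the last dose, a safety contact (AE review and C-SSRS, by telephone if needed) will take place 7–9 days after the last dose, if the subject agrees.*
2. In sections 3.6.1.1 and 5.1.1, end AE and SAE reporting at Visit 5 for subjects who finish and, for early leavers, at the later of the Early Termination Visit and that contact, or at death if sooner.
3. Optional: in sections 3.6.1.2 and 5.6, state that a subject stopped for QTc whose early termination ECG is still prolonged has a repeat ECG about one week after stopping. This matches the one-week ECG already required after a dose reduction for QT prolongation (2.3, 3.6.1.2), and mostly puts a date on an existing follow-up duty.

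The cost is one short contact per early leaver seen before day 7, at most about 0–3 of 15 on the assumptions above, plus an occasional ECG visit if item 3 is adopted. The site already telephones subjects weekly during ramp-up (3.5.1.2), and the C-SSRS is rater-administered (3.6.1.5), so no new instrument is needed. Sample size and analyses do not change. The downside is that some early leavers will decline, so the contact should be requested and the refusals recorded.
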